NCT04958200

8/10/24

Alcohol Use and Chronic Pain among Primary Care Patients

Protocol and Statistical Analysis

PROTOCOL

Design. The study was a block randomized two-group, between-subjects design. Participants were randomized to one of two intervention conditions (i.e., Smartphone Intervention Program vs. Treatment-as-Usual Control) following baseline based on a block randomization schedule stratified by sex at birth and level of heavy drinking (+/- 5 heavy drinking episodes).

Inclusion/Exclusion. Eligible participants were 18 years of age or older, fluent in English, engaged in primary care (i.e., had a primary care physician), experienced chronic non-cancer related pain, and reported heavy drinking. The chronic pain inclusion criterion was pain of moderate severity or greater in the past week that lasted for at least 3 months. Heavy drinking was determined by past month drinking that exceeded NIAAA limits (>7 for women > 14 for men) and/or the occurrence of one or more heavy drinking episodes in the past month.

Participants currently using pharmacological approaches for pain or alcohol use were permitted in the study if medication doses were stable for at least two months. Exclusion criteria were: history of bipolar disorder/schizophrenia/ complicated alcohol withdrawal, psychological treatment for pain or alcohol use within the past 3 months, and planned surgery for a pain-related condition in the subsequent six months. Participants were also excluded if they did not have a smartphone.

Recruitment. Recruitment took place within primary clinic waiting rooms [in a large urban](#) hospital, through recruitment letters sent to patients from a hospital data base by permission of primary care provider, and social media. Patients from hospital-based recruitment efforts who expressed interest were then screened by phone. Study advertisements delivered through social media were linked to a preliminary, web-based screening form. Individuals who met initial eligibility criteria based on the web-based screening were contacted by a member of the research team for phone screening to determine eligibility.

Assessments

Sample characteristics. Participants completed a series of measures to assess demographic characteristics including race/ethnicity, marital status, education, and employment.

Pain outcomes. The primary pain outcome for the trial was the Pain, Enjoyment of Life, and General Activity (PEG; Krebs et al., 2009). Participants rated the severity of their pain and the degree to which their pain interfered with enjoyment in life and general activity “in the past 7 days” using 0-10 scales. The PEG has excellent reliability and validity and has been widely established with medical populations. Secondary pain outcomes were past week pain severity rated on an 11-point scale and pain interference composite scores from the Brief Pain Inventory-Short Form (BPI) (Dworkin et al., 2005).

Alcohol outcomes. The primary alcohol outcomes were frequency of heavy drinking episodes (women > 3 per occasion, men > 4 per occasion) in the past 30-days and mean number of drinks per week as assessed by the 30-day alcohol Timeline Follow-Back calendar method (Alcohol TLFB-30) (Sobell et al., 1979). Alcohol-related consequences were assessed with the Short Inventory of Problems-Revised (Kiluk et al., 2013).

Additional outcome assessments. Participants completed additional assessments to examine the transdiagnostic effects of the intervention including depressive symptoms with the PHQ-8 (Kroenke et al., 2009), days of cannabis use in the past 30 days (Rosen et al., 2000) and physical functioning from the PROMIS-29 v2.0 (Hays et al., 2018).

Feasibility, acceptability, health behavior change processes. A series of assessments were taken approximately 8-weeks following baseline to assess participant experiences with the intervention conditions and assess health behavior change. All participants completed indices of intervention satisfaction using a modified version of the *Client Satisfaction Questionnaire-8* (CSQ-8), an 8-item validated measure of perceived value of treatment services (Kelly et al., 2018; Larsen et al., 1979). In addition, we used study specific Likert-type items based on the *Perceptions of Treatment Questionnaire (PTQ-17)*, (Pincus et al., 2010) that provides descriptive

information about perceived comprehensibility and utility of the intervention. Finally, to provide initial data regarding hypothesized mechanisms underlying the intervention, we utilized pain and alcohol specific measures of the Goal Systems Assessment Battery (Karoly and Ruehlman, 1995). Participants rated their self-regulatory processes related to the behavior change goals of “pain management” and “moderating/limiting alcohol use” using 4-point 16-item Likert-scale measures (“not at all” to “very much”). To gather usability and acceptability data on the smartphone intervention itself, we examined rates of completion for the video modules, adherence to health coach instant messaging sessions, and completion of smartphone daily activities to assess intervention acceptability. We also assessed whether participants engaged with the optional skills library. Participants in the smartphone intervention condition also completed 3-items selected from the *Systems Usability Scale* (Brooke, 1996) to provide information about the experience of program use through subjective ratings

Conditions

Smartphone Intervention Program [MCBMAP Intervention (INTV)]. The intervention utilized a self-regulation framework (Karoly, 2012) to integrate evidence-based approaches for hazardous drinking and pain including Motivational Interviewing (Miller and Rollnick, 2013) and cognitive-behavioral and self-management training (Morgenstern et al., 2007; Otis, 2007; Ruehlman et al., 2012; Sobell and Sobell, 1996). Participants first met with the health coach, who introduced the program, reviewed participants’ experience of pain and prior treatment, provided psychoeducation on the interaction between pain and alcohol use, and presented the program rationale. Participants were then provided access to the smartphone app. Intervention content was delivered through a series of app-based video modules that were supplemented with a brief (15 minute) weekly health coaching session delivered through instant messaging. Each of the eight intervention weeks were conducted through the app and included viewing one or two short video modules, completing two daily check-in and activity surveys. In addition,

participants had access to a Skills Library which contained a brief summary of each of the skills learned throughout the program.

Control (CTL). Those in the CTL condition completed a single videoconferencing session with the health coach which consisted of a brief review of the participant's pain and treatment history, psychoeducation about the interactive effects of pain and alcohol, discussion of resources available for pain and alcohol use, and the option to review information regarding available local and web-based behavioral health and wellness resources to address pain and alcohol use. These procedures are consistent with a treatment-as-usual-strategy to address these conditions in the clinic setting with available resources.

Training, supervision and fidelity assessment. The health coaches were advanced level PhD clinical psychology students who were trained for content related to both conditions. Supervision was provided biweekly and involved individual discussion of ongoing cases. Intervention fidelity assessment was conducted through a checklist of session components (specific to condition) conducted by research assistants based on audio-recordings and instant messaging transcripts.

Procedures

Participants were screened by phone and, if eligible, scheduled for an initial visit conducted through a videoconferencing platform. During the initial visit, participants were consented, completed a 50-minute baseline assessment, and were then randomized to the Control or Intervention condition. Participants then met with a study health coach for approximately 20 minutes through the videoconferencing platform. Those randomized to smartphone intervention program concluded the initial videoconferencing visit by downloading the study smartphone application and learning the procedures for using the app. The post-intervention and primary follow-up assessments were conducted 8 and 16-weeks following baseline respectively by a research assistant who was blind to study condition. All assessments were conducted using a videoconferencing interviewing assessment method supplemented with

on-screen displayed measures. Study data were collected and managed using REDCap electronic data capture tools (Harris et al., 2009). Participants were compensated for their time and effort related to assessments and paid \$50 for each assessment session.

Participants in the smartphone intervention condition, completed 8-weekly video-modules to learn new skills through the app and then completed two daily surveys to practice skills and evaluate outcomes over the subsequent week. Brief (approximately 15 minute) weekly health coaching sessions conducted through text messaging were scheduled to reinforce learning, identify barriers, and support program engagement. Participants were provided with technology support via a “troubleshooting” form designed for the program and the study research assistant. Participants were reminded via text message the day before and the day of each weekly instant messaging health coaching session.

STATISTICAL ANALYSES

The goals of this study were to provide information about the feasibility and acceptability of the intervention and preliminary information about the utility of this approach for reducing pain and heavy drinking (primary outcomes). Descriptive analyses provided information about intervention engagement, usability, and satisfaction while effect size estimates were computed to provide preliminary information about intervention efficacy.

Feasibility of methods and procedures were evaluated with descriptive data on the percent of patients screened, percent of eligible patients enrolled, and percent of patients who completed assessments. For those in the Intervention condition, adherence rates for the percent of modules completed and the percent of coaching sessions attended were assessed. Patient satisfaction with the intervention and treatment adherence, mean and median treatment satisfaction ratings were calculated based on measures described above.

Analyses of intervention impact were based on the full sample of participants who completed baseline and were randomized to condition. Lost to follow-up primary and secondary outcomes was defined as missing the 16-week assessment. For the primary analyses (i.e., PEG, heavy drinking, weekly drinking), multiple imputation was used to address missing outcome data and the full randomized sample was included. Completer analyses were conducted as sensitivity analyses for the primary outcomes and for all remaining outcomes. We estimated effect sizes using f^2 calculated from regression analyses, controlling for corresponding baseline values. For pain analyses, we also followed recommendations from the IMMPACT trial (Turk et al., 2008), and examined the percent of participants who exhibited moderate clinical improvement based on reductions of 30% and substantial clinical improvement based on 50% reduction in PEG scores.

Because the primary alcohol outcomes (i.e., number of heavy drinking episodes, number of drinks per week) were skewed, transformations to drinking data were required to provide an effect size estimate to parallel pain outcomes (i.e., f^2). To reduce the effects of extreme values,

one drinking quantity outcome greater than 3 SD was recoded to one greater than the next largest value (Tabachnick and Fidell, 2013). Alcohol outcomes were square root transformed in each analysis. Due to sex differences in consumption, analyses with alcohol outcomes were conducted with sex at birth as a covariate along with the corresponding baseline alcohol variable. Pooled estimates from multiple imputations were used for each of these primary outcomes.

REFERENCES

Brooke, J., 1996. Usability evaluation in industry. Taylor and Francis, London.

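### The plan aims to learn whether pain and heavy drinking were reduced, but the only model-based effect size it names is f², which has no sign or unit, and it commits to no interval

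*Combined protocol and SAP*

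**What the plan says.** The opening of the Statistical Analyses section gives a directional efficacy aim: "preliminary information about the utility of this approach for reducing pain and heavy drinking (primary outcomes". It then divides the work: "Descriptive analyses provided information about intervention engagement, usability, and satisfaction while effect size estimates were computed to provide preliminary information about intervention efficacy". Efficacy is thus left to the effect sizes.

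The measure is named later in the same section: "We estimated effect sizes using f^2 calculated from regression analyses, controlling for corresponding baseline values". For drinking, the same measure drives the choice of scale, since "transformations to drinking data were required to provide an effect size estimate to parallel pain outcomes (i.e., f^2", and "Alcohol outcomes were square root transformed in each analysis". Sex at birth and the baseline drinking value are covariates.

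For PEG there is one further summary: the plan "examined the percent of participants who exhibited moderate clinical improvement based on reductions of 30" percent, and likewise for 50 percent.

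On missing data, the primary outcomes are analysed in the full randomized sample with multiple imputation. "Pooled estimates from multiple imputations were used for each of these primary outcomes", without naming the quantity pooled. Completers have a supporting role: "Completer analyses were conducted as sensitivity analyses for the primary outcomes and for all remaining outcomes".

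The Procedures section makes the 16-week assessment the primary follow-up. Nowhere does the document mention a coefficient for condition, an adjusted mean difference, a standard error, a confidence interval or a drinking summary by arm.

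**The concern.** An aim of reducing something needs an estimate that can tell a reduction from an increase. f² for a single model term is a squared quantity: it records how much outcome variation the arm explains, not which arm did better. It is also unitless. For drinking it is computed on square roots, so it cannot be read back as episodes or drinks.

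For two of the three primary outcomes nothing else is committed. A report that followed the plan to the letter could give a drinking f² without saying whether the intervention arm drank less or more, or how uncertain the estimate is. For PEG, responder percentages by arm would reveal direction, but neither they nor f² come with an interval.

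The yield of a preliminary trial is direction, size and uncertainty for planning the next one. The fitted regressions already contain a signed arm coefficient, so the gap is in planned reporting and not in the data.

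**Working it through.** The document gives no sample size, standard deviation, correlation or target effect, so there is no figure of its own to reproduce. Everything numerical below is illustration, assuming equal arms, N = 50, 100 or 200, and r for the within-arm correlation between baseline and outcome.

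**1. Sign.** In a regression of outcome on baseline and arm, f² for the arm term is t²/df, where t is the coefficient over its standard error and df is N−3 for pain or N−4 for drinking (which adds sex). Squaring removes the sign. In population terms, for an arm difference d in within-arm SDs, f² = 0.25d²/(1−r²). With r = 0.5, d = −0.5 and d = +0.5 both give 0.25 × 0.25/0.75 = 0.083. With d = ±0.3 the value is 0.025, 0.030 or 0.044 at r = 0.3, 0.5 or 0.7, whichever arm is favoured.

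**2. How often direction matters.** The chance that the estimate falls on the harm side despite a true benefit is P(noncentral t < 0), with noncentrality √(f²N).

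| True f² | N = 50 | N = 100 | N = 200 |
|---|---|---|---|
| 0.02 | √1.0 = 1.00; 15.9% | √2.0 = 1.41; 7.9% | √4.0 = 2.00; 2.3% |
| 0.05 | √2.5 = 1.58; 5.7% | √5.0 = 2.24; 1.3% | √10.0 = 3.16; 0.1% |

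These rates follow from sample size. A signed coefficient would land on the wrong side equally often, but the reader would see it.

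**3. Precision.** The 95% sampling range of f² is the 2.5% and 97.5% points of noncentral F(1, df), noncentrality f²N, divided by df. For true f² = 0.05:

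| N | Pain | Drinking |
|---|---|---|
| 50 | 0.0003–0.29 | 0.0003–0.30 |
| 100 | 0.001–0.19 | 0.001–0.19 |
| 200 | 0.007–0.14 | 0.007–0.14 |

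With no effect at all, the expected sample f² is 1/(df−2). For pain that is 1/45 = 0.022, 1/95 = 0.011 and 1/195 = 0.005, so a small f² without an interval cannot be told from noise.

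**4. Units on the square-root scale.** From an assumed control level c, a reduction of 0.5 root units is c − (√c − 0.5)² in raw units. For drinks per week that is 4 − 2.25 = 1.75 at c = 4, 16 − 12.25 = 3.75 at c = 16, and 36 − 30.25 = 5.75 at c = 36. One effect on the analysis scale therefore covers quite different changes in drinking.

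**5. What a signed estimate would show.** With complete data and r = 0.5, the half-width of a 95% interval is t(0.975, N−3) × √0.75 × 2/√N. This gives 0.49, 0.34 and 0.24 SD at N = 50, 100 and 200. A simulation assumed 20% missing completely at random, 20 proper normal imputations, r = 0.5, true f² of 0, 0.05 and 0.15, and 2000 trials per setting. The coefficient pooled by Rubin's rules had interval coverage of 94.7–95.4% in all nine settings, with half-widths of about 0.57, 0.39 and 0.27 SD.

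**The case against.** **The plan is short, and silence is not exclusion.** Regressions were fitted, and the pooled estimates may well include coefficients. A report may also give means by arm. This is fair, and it limits the claim: the planned reporting need not show direction or precision. A reader might infer that direction cannot be recovered or that the report will hide it. The document supports neither.

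**The aim is only preliminary.** That excuses the lack of a hypothesis test. It does not make an unsigned measure without an interval sufficient, because direction and uncertainty are what a preliminary trial hands on.

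**The PEG responder percentages are clinically readable.** They are, and they can show direction for pain. They have no drinking counterpart and no stated interval.

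**Perhaps f² is for the whole model.** A reader might infer this, since the term is unnamed. With no intervention effect, r²/(1−r²) would then give 0.10, 0.33 or 0.96 at r = 0.3, 0.5 or 0.7. But the text speaks of intervention impact, adjusts for baseline and calls sex a covariate, all of which point to the arm term. It is an ambiguity to close with a few words, not evidence of a misleading measure.

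**Perhaps f² should come from the completers.** A reader might infer this on the ground that Rubin total variance shrinks f². The plan makes the imputed full sample primary and completers a sensitivity analysis. In the simulation above, at true f² = 0.05, the mean f² at N = 50, 100 and 200 was 0.062, 0.053 and 0.045 using Rubin variance, and 0.081, 0.068 and 0.057 in completers. Rubin-based f² is not generally below the truth, and completers overshoot in every case.

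**Conclusion.** The point stands as a gap in planned reporting that should be fixed. For heavy drinking episodes and drinks per week, the only committed effect size has no sign and no unit, and nothing committed shows direction or precision. For PEG, direction can be seen from the responder percentages, but precision is not committed. This holds under the natural arm-term reading and does not depend on the term being unnamed.

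Confidence in the omission is high, because it rests on the text alone. The numbers are less firm: N, correlation, effect size and missingness are all assumed, so they show the kind of consequence and do not measure a defect in this trial. Nothing here questions the regression models, the transformation, the covariates or the use of multiple imputation.

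**What to change.** 1. For each primary outcome, make the main estimate the baseline-adjusted intervention-minus-control difference at 16 weeks with a 95% confidence interval, pooling the coefficient and its variance over imputations by Rubin's rules.
2. Give PEG in points. Give drinking on the square-root analysis scale with sex as covariate, plus raw summaries by arm in episodes per 30 days and drinks per week. If size in usable units is wanted with its uncertainty, add a raw-scale difference between arms with a 95% interval.
3. Report the 30% and 50% PEG responder percentages by arm, with the difference and its 95% interval, computed in each imputed data set and then pooled.
4. Keep f² as a secondary descriptor. State that it is for the arm term, show it with the sign of the coefficient, compute it in the multiply imputed full sample, and say how it was pooled.

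**Cost.** Item 1 and the square-root results are output from models already fitted. The responder differences need their own estimate in each imputation, and a raw-scale difference would need its own analysis. No new data are required. As the document is written in the past tense, this is in practice a clarification of reporting. The downside is that wide intervals are shown openly.

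### The f² effect size is biased upward at small N, carries no sign or confidence interval, and has no stated rule for pooling it over imputations

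*Combined protocol and SAP*

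**What the plan says.** All of this is in the STATISTICAL ANALYSES section of the combined protocol and SAP, except the design statement.

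- Purpose: "effect size estimates were computed to provide preliminary information about intervention efficacy".
- Estimator: "We estimated effect sizes using f^2 calculated from regression analyses, controlling for corresponding baseline values". For the drinking outcomes, "analyses with alcohol outcomes were conducted with sex at birth as a covariate along with the corresponding baseline alcohol variable", after a square-root transformation.
- Missing data, for the PEG, heavy drinking and weekly drinking: "multiple imputation was used to address missing outcome data and the full randomized sample was included". The section closes with "Pooled estimates from multiple imputations were used for each of these primary outcomes". Completer analyses serve as sensitivity analyses for these outcomes and as the only analyses for the rest.
- Design (PROTOCOL, Design): "The study was a block randomized two-group, between-subjects design".

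The documents do not give the number randomized, the dropout rate, the number of imputations, or the quantity that is pooled. They do not say that f² is the partial f² for the arm term. They mention no small-sample correction, confidence interval or direction for f².

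**The concern.** A squared effect size averages above zero when the intervention does nothing, and the excess grows as the sample shrinks. In a study of this kind the excess may be as large as an effect that a reader would call small. The value also has no sign, so it does not show which arm did better. For the PEG, the 30% and 50% improvement percentages partly fill that gap. For the two drinking outcomes no other efficacy measure is described.

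Imputation adds a second issue. f² can be combined over imputed data sets in several ways, and these give different answers from the same data. The usual averaging rule suits estimates that are roughly normal, which a squared quantity near zero is not.

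At stake is how the pilot's efficacy results are read, by this team and by anyone who later uses the published f².

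**Working it through.** The plan states no figure for f², N or power, so there is nothing of its own to reproduce.

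**Inputs from the documents.** Two arms. The PEG model has an intercept, arm and baseline (p = 3). The drinking models add sex at birth (p = 4).

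**Assumptions.** f² is the partial f² for arm; allocation is 1:1; N runs from 30 to 150. The simulations use normal outcomes, baseline correlation 0.5, outcomes missing completely at random and 20 proper regression imputations.

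**Step 1: no effect, complete data.** For a one-degree-of-freedom term, f² = F/ν with ν = N − p. Since F(1, ν) has mean ν/(ν − 2), the mean of f² is 1/(ν − 2).

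| N | PEG model (p = 3) | Drinking models (p = 4) |
|---|---|---|
| 30 | 1/25 = 0.040 | 1/24 = 0.042 |
| 50 | 1/45 = 0.022 | 1/44 = 0.023 |
| 80 | 1/75 = 0.013 | 1/74 = 0.014 |
| 100 | 1/95 = 0.0105 | 1/94 = 0.0106 |
| 150 | 1/145 = 0.007 | 1/144 = 0.007 |

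This bias does not depend on how imputations are pooled.

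**Step 2: a true effect.** Take true f² = 0.0625 and N = 50. The mean of the sample f² is (1 + N × f²)/(ν − 2) = (1 + 3.125)/45 = 0.092.

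**Step 3: imputation, N = 50, no effect.** Let b be the pooled arm coefficient, W the mean within-imputation variance, B the between-imputation variance and T Rubin's total variance. Averaging f² over data sets gives roughly (b² + B)/(ν × W), so B enters as if it were signal. The completer means follow from step 1 with the smaller sample: 1/(42.5 − 5) = 0.027 at 15% missing and 1/(37.5 − 5) = 0.031 at 25%.

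| Missing | Completers | f² averaged (simulated) | Rubin-pooled t, t²/ν (simulated) |
|---|---|---|---|
| 0% | 0.022 | 0.022 | 0.022 |
| 15% | 0.027 | about 0.03 | about 0.022 |
| 25% | 0.031 | about 0.04 | about 0.022 |

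**Step 4: the same question with true f² = 0.0625, N = 50, 25% missing.** Averaged f² reads about 0.108. The completer expectation is (1 + 37.5 × 0.0625)/32.5 = 0.103. The Rubin-pooled t gives about 0.070, down from about 0.09 with no missing data, because T grows as data are lost.

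**Step 5: the adjusted form.** For completers, use (t² − 1)/ν. Its no-effect mean is 2/(ν(ν − 2)) = 2/(47 × 45) = 0.001 at N = 50. For imputed data, use (b² − T)/(ν × W), which reduces to the completer form when nothing is missing, since then T = W and b²/W = t². In simulation at N = 50 its no-effect mean was within about 0.003 of zero at 0, 15 and 25% missing. With true f² = 0.0625 it read 0.069 to 0.072. The complete-data expectation is 0.092 − 1/47 = 0.070.

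Precision does not suffer. With no effect and complete data at N = 50, the mean square of the raw f² is 3/(45 × 43) = 0.00155, a root mean squared error of 0.039. The adjusted form has the same variance, 0.00155 − 0.022² = 0.00106, and almost no bias, so its root mean squared error is about 0.0325.

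**The case against.** The strongest reply is that this is a feasibility pilot with descriptive effect sizes and no test or decision rule. Much of that stands, and it limits what can be claimed. Five stronger readings are tempting, and the documents support none of them.

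- A reader might infer that the plan averages f² over imputations. It says only that pooled estimates were used. That fits equally well with pooling the coefficient first and deriving f² from it, in which case the extra inflation can vanish.
- A reader might infer that a no-effect value of 0.02 to 0.04 is what this trial should expect. With complete data that needs N of about 30 to 55. At N = 100 to 150 the figure is 0.0105 to 0.007, and N is not stated.
- A reader might infer that chance values would be declared efficacy. Against an assumed benchmark of 0.02, a no-effect PEG f² exceeds it 34% of the time at N = 50 and 9% at N = 150. The documents set neither that benchmark nor a success rule.
- A reader might blame averaging for most of the 0.108 in step 4. The completer value is already about 0.10, so averaging adds only about 0.005. The rest of the excess over 0.0625 is ordinary small-sample bias, enlarged by the lost observations.
- A reader might infer that a follow-on trial will be sized from f² and come out too small. The documents do not say so.

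The improvement percentages for the PEG also do not rest on f². None of this removes the bias in step 1 or supplies the missing pooling rule.

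**Conclusion.** The point holds in a limited form. As stated, the estimator is biased upward by about 1/(ν − 2) when there is no effect: 0.040 at N = 30 down to 0.007 at N = 150. This rests on f² being the partial value for arm and on normal-theory regression. The size for this trial cannot be fixed without N.

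The further inflation from imputation is conditional. It arises if f² itself is averaged, and its size depends on the assumed dropout, the missing-completely-at-random mechanism and the imputation model. Using the 8-week score in the imputation model could reduce it. What the documents do show is that the pooling of f² is unspecified, and that the possible rules give materially different values.

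This is a cheap improvement to estimation and reporting. It does not show that any reported effect is false.

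**What to change.** 1. State that f² is the partial f² for arm. Pool the arm coefficient and its variance by Rubin's rules first, and do not average f² or R² over imputations.
2. Report the bias-adjusted value, (b² − T)/(ν × W) for imputed analyses and (t² − 1)/ν for completer analyses. Keep negative values as computed. A negative value reflects noise around a small effect and should not be relabelled as evidence of no effect.
3. Print 1/(ν − 2) at the actual N beside any unadjusted f².
4. Give the signed adjusted arm difference with a 95% confidence interval for each primary outcome, noting the square-root scale for the drinking outcomes.

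**Cost.** A few lines of code and text, with no new data. Reported effect sizes become smaller, and some will be at or below zero. The adjusted form is not exactly unbiased: with a true effect it still reads slightly high, about 0.070 for a true 0.0625 at N = 50.

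### Does recoding one extreme drinking value, with no analysis that keeps the observed value, undermine the drinks-per-week effect size?

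*Combined protocol and SAP*

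**What the plan says.** Under Alcohol outcomes, one of the two primary alcohol measures is "mean number of drinks per week as assessed by the 30-day alcohol Timeline Follow-Back calendar method"; the other counts heavy drinking episodes. The STATISTICAL ANALYSES section says both were skewed and needed transforming so that an f² comparable with the pain results could be computed. It then describes two steps:

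- "To reduce the effects of extreme values", "one drinking quantity outcome greater than 3 SD was recoded to one greater than the next largest value", with a statistics textbook cited for the rule.
- "Alcohol outcomes were square root transformed in each analysis".

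The models adjust for the baseline alcohol measure and sex at birth, and "Pooled estimates from multiple imputations were used for each of these primary outcomes". On sensitivity work the section says only: "Completer analyses were conducted as sensitivity analyses for the primary outcomes and for all remaining outcomes". The purpose of the estimates is also stated: "effect size estimates were computed to provide preliminary information about intervention efficacy".

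The section does not give the recoded participant's arm, the time point, the value before and after recoding, the scale on which 3 SD was judged, or whether the recode came before or after imputation.

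**The concern.** Two devices act on the same tail. The square root already pulls in large values, and one value was lowered as well, with no data error described. Drinking quantity most naturally means drinks per week, since the other primary alcohol measure is a frequency, so a primary result is affected.

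The completer analyses deal with participants missing at week 16, so they do not show what the recode did. The direction of the effect depends on facts not given. Lowering a follow-up value in the intervention arm moves the adjusted arm difference in the app's favour, and lowering one in the control arm moves it the other way. Because f² has no sign, the reported number would not reveal which happened. If the shift were large, the preliminary evidence on drinking could rest on one person.

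**Working it through.** **No figure to reproduce.** The documents state no sample size, SD, recoded value or f². Everything numerical below is therefore illustrative, with assumed inputs.

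**Can the rule operate?** The largest standardised value possible in a sample of n is (n − 1)/√n. At n = 10 this is 9/3.162 = 2.85; at n = 11 it is 10/3.317 = 3.02. One value beyond 3 SD is therefore possible in any sample of 11 or more, and nothing is odd about finding one.

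**What the recode does after the square root.** In the simulated samples of 40 with no true effect, the flagged value had a median of 51 drinks per week before recoding and 35 after. On the analysed scale that is √51 − √35 = 7.14 − 5.92 = 1.22 units for one participant, in place of 16 drinks on the raw scale.

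**Effect on f².** From the plan: square root of drinks per week, adjusted for square-root baseline and sex. Assumed: 1:1 allocation, lognormal drinking, baseline to follow-up correlation of about 0.6 on the log scale, true f² of 0, 0.02 or 0.05, complete data. Only samples with exactly one follow-up value above mean + 3 SD on the untransformed scale were kept. That value was set to the second largest plus one. The arm effect is

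f² = (SSE without arm − SSE with arm) / SSE with arm,

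computed once with the observed value and once with the recoded value. Results for a true f² of 0.02:

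| N | Median shift in f² | 95th percentile of shift | Sampling SD of f² | Median shift / SD | 95th percentile / SD |
|---|---|---|---|---|---|
| 40 | 0.0044 | 0.0339 | 0.069 | 0.06 | 0.49 |
| 60 | 0.0028 | 0.0213 | 0.046 | 0.06 | 0.46 |
| 100 | 0.0020 | 0.0125 | 0.033 | 0.06 | 0.38 |

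With no true effect both quantities shrink. At N = 100 the median shift is 0.0015 against an SD of 0.0136, a ratio of 0.11. Across N of 40 to 200 and all three true effects, the median shift is 0.001 to 0.005. The recode carries f² across an assumed benchmark of 0.02 in 2 to 10% of samples.

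**Direction.** With a true benefit assumed, recoding an intervention-arm value raised f² by 0.005 to 0.015 on average. Recoding a control-arm value changed it by between 0 and −0.003. The sign therefore does depend on the unreported arm, but these averages are also small beside the sampling SD.

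**What could turn on it.** The STATISTICAL ANALYSES section sets no significance level, no f² threshold and no rule for proceeding to a larger trial. A shift of this size has no stated decision to reverse.

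**The case for a change.** The strongest reply is that a small typical effect is not a known effect in this trial. At N = 40 the 95th percentile of the shift is 0.025 to 0.044, as large as a small effect, and the one analysis that would settle the matter is not described. The data are held, so a second run would cost little, plus a sentence or two. Order also matters: a recode made before imputation changes the data to which the imputation model is fitted, and the simulation above did not include missing data.

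All of that is true, and showing both f² values would be good reporting. It does not make the analysis as described unsound. The large shifts arise mainly in the smallest samples, where f² is least precise with or without the recode. Recoding the observed data before imputing is the ordinary order of work, and an analyst would not need to be told.

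A related argument is that a 3-SD check on skewed, untransformed data flags ordinary drinkers: under the assumed distributions, at least one value in 43 to 99% of samples. This fits poorly with a report of a single recoded value. If baseline and week 16 were both screened on that scale, exactly one flag would occur in only 1 to 44% of samples. The data may have been less skewed than assumed, or the check narrower or on another scale. The flag rates therefore do not show that an ordinary value was altered.

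Nor is there evidence that the arm influenced the recode: the rule as stated makes no reference to arm. Blinding of the follow-up assessor, stated under Procedures, protects measurement but does not bear on the recode decision.

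**Conclusion.** No change to the plan follows. It is correct that no analysis with the observed drinking value is described and that the recode's effect in this trial cannot be worked out from the document. But the recode is disclosed, with its reason, threshold, replacement rule and count. It keeps the participant in the analysis at the highest rank, and the square root further limits that value's influence. Under the assumed inputs, the typical shift in f² is 0.001 to 0.005, about 6% of its sampling SD when the true f² is 0.02 and about 11% with no effect at N = 100. No decision rule is attached to the estimate.

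Three things remain: unreported detail (arm, time point, scale of the check, order relative to imputation), a choice of scale for judging outliers on which statisticians reasonably differ, and a refit that would rarely alter a preliminary conclusion. The sizes rest on assumed sample sizes, lognormal drinking, a correlation of about 0.6, complete data, and the reading that the recoded value was a follow-up drinks-per-week value. A very small trial with a much more extreme value could show a larger shift.
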